9.10 Scoring of HRQoL data

As per NCCN-FACT FKSI-19 scoring guidelines (version 2), the total HRQoL score (range 0-76) will be calculated as sum of single items scores multiplied by 19 and divided by the number of items completed. NCCN-FACT FKSI-19 will also cover 4 subscales: DRS-P (items from 1 to 11, range 0-48), DRS-E (item 12, range 0-4), TSE (items from 13 to 15, range 0-12) and FWB (items from 16 to 19, range 0-12). The higher the sub-scores or the total score, the better the HRQoL. The subscales will be evaluable, if at least 50% of respective items will be answered and will be calculated as sum of items included in the subscale, multiplied by the item included in the subscale, and divided by the item answered in the subscale. The FKSI-19 questionnaire as a whole will be evaluable if all subscales will be evaluable and at least 80% of all items will be answered. Score of items 11 (C6), 12 (GF5), and from 16 to 19 (GF1, GF3 and GF7) will be reversed before calculating total and subscale scores.

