### **Patient-reported outcomes:**

- HRQoL using the NCCN-FACT FKSI-19 at the index date and at every third cycle of Avelumab treatment (intervals of about 6 weeks) thereafter until the end of treatment or end of 24 months of study follow-up, whichever occurs first
  - The NCCN-FACT FKSI-19 is a 19-item self-reported questionnaire that captures symptom severity and interference in activity and general health perceptions ([Rothrock 2013](#), [Rao 2009](#))
  - The NCCN-FACT FKSI-19 covers 4 subscales of the FKSI:
    1. DRS-P, disease-related symptoms subscale—physical
    2. DRS-E, disease-related symptoms subscale—emotional
    3. TSE, treatment side effects subscale
    4. Functional and well-being (FWB), function and well-being subscale ([Rao 2009](#))
  - Each of the items is scored on a five-point scale from zero (not at all) to 4 (very much).

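### As written, the FKSI-19 scoring rule runs against the plan's own higher-is-better direction, and its item lists do not fit its ranges for DRS-P and FWB

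*SAP*

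**What the plan says.** Protocol 9.1.2.2 (Patient-reported outcomes) sets the response scale: "Each of the items is scored on a five-point scale from zero (not at all) to 4 (very much". It names four subscales: physical disease-related symptoms (DRS-P), emotional disease-related symptoms (DRS-E), "TSE, treatment side effects subscale", and "Functional and well-being (FWB), function and well-being subscale".

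SAP 9.10 gives the scoring and attributes it to version 2 of the instrument's scoring guideline:

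- Direction: "The higher the sub-scores or the total score, the better the HRQoL".
- Item lists with ranges, first three subscales: "DRS-P (items from 1 to 11, range 0-48), DRS-E (item 12, range 0-4), TSE (items from 13 to 15, range 0-12".
- Item list with range, fourth subscale: "FWB (items from 16 to 19, range 0-12". For the total, the stated range is 0 to 76.
- Reversal: "Score of items 11 (C6), 12 (GF5), and from 16 to 19 (GF1, GF3 and GF7) will be reversed".
- Proration for missing items within a subscale: "sum of items included in the subscale, multiplied by the item included in the subscale, and divided by the item answered in the subscale".

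Protocol 9.7.2 (version 4.0) has the same item lists, ranges and reversal list. SAP 16.3 takes the total and subscales from SAP 9.10 into the descriptive summaries and the repeated-measures trend.

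**The concern.** There are two separate problems.

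**Direction.** If a higher score is to mean better health, items where *very much* is bad must be reversed and items where *very much* is good must not. The rule appears to do the opposite. It leaves all three side-effect items and ten of the eleven listed physical-symptom items raw, and it reverses every item assigned to function and well-being.

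**Items against ranges.** The DRS-P and FWB item lists cannot produce the stated ranges, and three item codes are given for four item positions (16 to 19). Two programmers could build different subscales and both claim to follow the plan.

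HRQoL is a named secondary objective. A trend with the wrong sign would report deterioration as benefit, and in a single-arm study there is no comparator whose result might expose it. The primary OS rate is not touched, and no FKSI-19 table is in the SAP's list of primary-analysis outputs (Section 18), so the exposure is at the final analysis.

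**Working it through.** **Inputs.** Response scale 0-4 and subscale names (protocol 9.1.2.2); item lists, ranges, reversal list, direction and proration (SAP 9.10, repeated in protocol 9.7.2). A reversed item scores 4 minus raw.

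**1. Reproducing the stated ranges** (maximum = 4 x number of items)

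| Subscale | Items listed | 4 x items | Stated maximum | Items the range implies |
|---|---|---|---|---|
| DRS-P | 1-11 (11) | 44 | 48 | 12 |
| DRS-E | 12 (1) | 4 | 4 | 1 |
| TSE | 13-15 (3) | 12 | 12 | 3 |
| FWB | 16-19 (4) | 16 | 12 | 3 |
| Sum | 19 | 76 | 76 | 19 |

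DRS-P and FWB do not reproduce. Both columns of maxima sum to 76 (44+4+12+16 and 48+4+12+12), so checking the total alone does not show the error. The three codes given for positions 16-19 favour the ranges. The consecutive split that would fit the ranges is 1-12, 13, 14-16, 17-19, but the documents do not confirm it.

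**2. Direction.** Reversed items: 11, 12, 16-19 (6). Raw items: 1-10, 13-15 (13).

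The item texts are not in the documents. Assumption, from the subscale names: items 1-10 and 13-15 are negatively worded and 17-19 positively worded. Items 11, 12 and 16 are left open, which gives 2 x 2 x 2 = 8 combinations.

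Let p be the number of positively worded items among the six reversed ones, here 3 to 6. In the worst health each raw negative item scores 4, each reversed positive item scores 4 - 0 = 4, and each reversed negative item scores 4 - 4 = 0. So:

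- worst-health total = 4 x (13 + p)
- best-health total = 4 x (6 - p)

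| p | Worst health | Best health |
|---|---|---|
| 3 | 64 | 12 |
| 4 | 68 | 8 |
| 5 | 72 | 4 |
| 6 | 76 | 0 |
| 0 (outside the assumption: no item positively worded) | 52 | 24 |

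By subscale as listed, worst against best health, for p = 3 to 6:

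- TSE: 12 against 0.
- DRS-P: 40-44 against 0-4.
- FWB: 12-16 against 0-4.
- DRS-E: 0 against 4 if item 12 is negatively worded (correct), otherwise 4 against 0.

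**3. What it would take for the total to run the right way.** Let k of the 13 raw items be positively worded. The worst-health total is 4 x ((13 - k) + p) and must fall below the midpoint, 76/2 = 38. So (13 - k) + p must be at most 9, that is k at least 4 + p. For p = 3 to 6, 7 to 10 of the 13 unreversed symptom and side-effect items would have to be positively worded. With p = 0 it would still take 4.

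**4. If the ranges are right and the item numbers wrong** (1-12, 13, 14-16, 17-19). TSE is then items 14 and 15 raw and item 16 reversed. If all three are negatively worded, the worst-health score is 4 + 4 + 0 = 8 and the best is 0 + 0 + 4 = 4. This is less extreme than 12 against 0 but still backwards. FWB (17-19, all reversed) is 0 for the best health and 12 for the worst. The total does not depend on the subscale split.

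**5. Proration.** The multiplier is the number of items in the subscale, so the item conflict carries through. Two FWB items answered with scored sum 6 give 6 x 4/2 = 12 with four items, or 6 x 3/2 = 9 with three.

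**The case against.** The strongest reply is that no item wording is printed, so part of the direction argument rests on labels. Protocol 9.1.2.2 says the instrument also covers interference in activity, so negatively worded function items cannot be excluded from the documents. If items 16-19 were all negatively worded, reversing them would be right. That stands: the FWB part is conditional, and the 64-76 against 0-12 range holds only under the stated assumption. It does not rescue the rule. With no positively worded item at all, the worst-health patient still outscores the best (52 against 24), and TSE (12 against 0) and DRS-P (40 against 4) still run backwards.

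It is also fair that not every worsening would be misreported. A change confined to reversed items that are negatively worded would lower the score as intended. And the proration example adds no separate harm: 12 of 16 and 9 of 12 are both 75% of the maximum, so it is the range mismatch seen again.

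Finally, the analyses are descriptive, the scores can be recomputed from item responses, and a programmer working from the guideline might query the rule. These points limit the damage. But the rule is presented as the guideline's content, and SAP 16.3 points to it, so scoring correctly would mean departing from the plan.

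**Conclusion.** The concern holds. The range mismatch is plain arithmetic: DRS-P can reach 44, not 48, FWB can reach 16, not 12, and three codes cover four positions. The conflict in direction for TSE and DRS-P follows from the response anchors and the subscale names. FWB runs backwards as well if its items are positively worded, as the name suggests. The total runs backwards under all eight combinations for items 11, 12 and 16 (worst health 64-76, best 0-12), and also if no item is positively worded (52 against 24).

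This rests on items 1-10 and 13-15 being symptom and side-effect statements. DRS-E as listed may be correct. Followed as written, broad worsening in the total would be reported as improvement in a secondary outcome. That is an error in the rule, not a missing detail, and it must be corrected before HRQoL is analysed. The primary endpoint is unaffected.

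**What to change.** In both SAP 9.10 and protocol 9.7.2:

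1. State that negatively worded symptom and side-effect items are reversed (4 minus raw) and that positively worded items, including those of FWB, are not.
2. Replace the item lists with a table of all 19 items giving code, subscale and a reversal flag, confirmed against the cited scoring guideline (version 2). Settle there the polarity of items 11 (C6), 12 (GF5) and 16 and the item-to-subscale map, so that items, codes, ranges and proration multipliers agree. Simply swapping the reversed and raw sets is not safe: under the same assumption, the best-health patient would then score 52 + 4p, which is 76 only if p = 6 and just 64 if p = 3.
3. Before the HRQoL analysis, require a programmed check that the best-health response pattern scores 76, the worst scores 0, and the subscale maxima equal the confirmed ranges (48, 4, 12 and 12 if the stated ranges are right).

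The cost is a wording change in two documents and one programming check. No new data are needed.

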9.11 Further subsections

Not applicable.

10 Study Participants

The subsections in this section include specifications for reporting participant disposition and study treatment/study discontinuations. Additionally, procedures for reporting protocol deviations are provided.

10.1 Disposition of Participants and Discontinuations

This section describes how participant disposition, study and study treatment discontinuations will be summarized.

The number and percentage of participants in each of the below disposition categories will be presented:

- Total number of participants screened (i.e. participants who gave informed consent)
- Number of participants who did not continue beyond screening, overall and grouped by the main reason (using the reasons as collected in the categories of the eCRF Study Entry Form: Subject did not meet all eligibility criteria, Withdrawal by subject, Other). The corresponding percentage will be calculated using the number of screened participants as a denominator.

For the following categories, the corresponding percentage will be calculated with respect to the number of enrolled participants:

- Number of participants who completed each treatment of the combination (considering the information collected through the eCRF Treatment Termination Form)
- Number of participants who discontinued each treatment of the combination, overall and grouped by main reason (with reason collected through the eCRF Treatment Termination Form). The percentages for the reasons will be calculated using the number of participants who discontinued each treatment of the combination as denominator
- Number of participants ongoing with reference to each treatment of the combination at the data cut (considering the information collected through the eCRF Treatment Termination Form)
- Number of participants who completed the study (considering the information collected through the eCRF Study Termination Form)
- Number of participants who discontinued the study, overall and grouped by main reason (with reason collected through the eCRF Study Termination Form). The percentages for the reasons will be calculated using the number of participants who discontinued the study as denominator
- Number of participants ongoing with reference to the study at the data cut (considering the information collected through the eCRF Study Termination Form)

For the participants discontinuing the study a listing with the following variables will be presented:

- Patient number
- Index date
- Last Avelumab and last Axitinib administration date
- Status at the EOT(Completed/ Permanently discontinued)
- Study discontinuation Date
- Primary reason for study discontinuation
- If Withdrawal by subject, specify
- If Other, specify.

Primary reason for study discontinuation will include Coronavirus disease 2019 (COVID-19) as possible reason evaluating the AEs description or the additional specification reported in study discontinuation form when “Adverse Events” or “Other” reasons will be selected.

For the participants permanently discontinuing the treatment a listing with the following variables will be presented:

- Patient ID

- Index start date
- Last Avelumab and last Axitinib administration date
- Primary reason for treatment termination
- If Withdrawal by subject, specify
- If Other, specify.

Primary reason for study treatment discontinuation will include COVID-19 as possible reason evaluating the AEs description or the additional specification reported in Avelumab and/or Axitinib discontinuation form when “Adverse Events” or “Other” reasons will be selected.

A separate disposition table with focus on COVID-19 impact will be presented including the following descriptive statistics:

- Participants potentially affected by COVID-19
- Total COVID-19 related protocol deviations (important and minor)
- Participants with at least one COVID-19 related protocol deviation (important and minor)
- Participants who discontinued any study treatment for reasons related to COVID-19
- Participants who discontinued the study for reasons related to COVID-19
- Participants with AEs related to COVID-19
- Participants with cause of death related to COVID-19

A subject potentially affected by COVID-19 will be defined as subject who started treatment after the start of the COVID-19 pandemic, or subject who started treatment prior to start of the COVID-19 pandemic and is still ongoing after the start of the pandemic. The start of COVID-19 pandemic is defined as the earliest date of either: (1) the date of the first death attributed to COVID-19 in the patient’s country, according to the published data by European Centre for Disease Prevention and Control on 26th June 2020 or (2) 11th March 2020 (when the WHO declared COVID-19 pandemic).

10.2 Protocol Deviations / Exclusion from Analysis Sets

10.2.1 Important Protocol Deviations

Important protocol deviations (IPDs) are protocol deviations that might significantly affect the completeness, accuracy, and/or reliability of the study data or that might significantly affect a participant's rights, safety, or well-being.

IPDs include:

- Participants enrolled on the study who did not satisfy enrolment criteria
- Participants that develop withdrawal criteria whilst on the study but are not withdrawn
- Participants that receive an incorrect dose
- Failure to collect data necessary to interpret primary endpoints
- Failure to collect necessary key safety data
- Any other protocol deviation that might significantly affect the completeness, accuracy, and/or reliability of the study data or that might significantly affect a participant's rights, safety, or well-being.

IPDs will be identified for all participants by either site monitoring, medical review processes or programming and confirmed prior to or at the Data Review Meeting at the latest.

Clinically IPDs are a subset of IPDs that could impact the key objectives of the study and that would lead to the exclusion of a patient from an analysis set (see [Section 8.1](#) Definition of Analysis Sets).

Clinically IPDs may be identified during the course of the study but will not require amendments to this IAP.

IPDs will be summarized for:

- Deviations from the inclusion and exclusion criteria
- Deviations post inclusion

A frequency table for IPDs, organized according to whether the protocol deviation is a pre-/post inclusion deviation, as well as a listing of IPD, will be provided based on the analysis set.

Protocol deviations attributed to the impact of COVID-19 pandemic will be labeled accordingly. Both important and non-IPDs attributable to the COVID-19 pandemic will be included and summarized.

A listing including protocol deviation impacted by COVID-19 will be also provided.

10.2.2 Reasons Leading to the Exclusion from an Analysis Set

A frequency table organized according to reason for exclusion from the analysis set, as well as a listing, will be provided.

11 Demographics and Other Baseline Characteristics

If not stated otherwise, the following analyses will be performed based on analysis set overall.

11.1 Demographics and Baseline Characteristics

Demographic characteristics and physical measurements will be summarized descriptively using the following information from the Screening/Baseline Visit eCRF pages.

- The following characteristics will be included:
 - Sex: male, female, other
 - Age (years)
 - Age categories: < 65 years, 65-75 years and >75 years
 - Baseline Systolic blood pressure and diastolic blood pressure (millimeters of mercury)
 - Baseline Pulse (beats per minute).
 - Baseline Weight (kilogram)

Specifications for computation:

- Age [years]: *(year of given informed consent - year of birth)*.
- To convert weight collected in pounds to kilogram, the conversion factor 0.45359237 will be used.

11.2 Medical History

The medical history will be summarized from the “Medical History” eCRF page, using MedDRA version 24.0 or higher, PT as event category and SOC body term as Body System category. Each participant will be counted only once within each PT or SOC.

Medical history will be displayed in terms of frequency tables: ordered by primary SOC and PT in alphabetical order.

11.3 Other Baseline Characteristics

Information on disease and disease related characteristics collected at baseline will be summarized.

Summary statistics will be presented for:

- Site of primary tumor (including sub-sites)
- Location of metastases
- Age at diagnosis (years)
- Time from initial diagnosis to documented, locally advanced, inoperable or metastatic disease diagnosis (years)
- Histopathological classification (clear cell, sarcomatoid, other)
- Tumor, node, metastasis (TNM) status at initial diagnosis and tumor staging derived as described in table below:

Stage	TNM
I	T1, N0, M0
II	T2, N0, M0
III	T3, N0, M0 or T1 to T3, N1, M0
IV	T4, any N, M0 or T4, any N, M1

The following additional categories are not listed in the table above:

- T0: There is no evidence of a primary tumor.
- NX: Nearby lymph nodes cannot be assessed due to lack of information.
- TNM status at study entry
- Prior nephrectomy (Yes/No)
- Expression of PD-L1 (Positive/Negative)
- MSKCC risk group (0 - low, 1 or 2 - intermediate, ≥ 3 - high)
- IMDC risk group (0 - low, 1 or 2 - intermediate, ≥ 3 - high)
- ECOG PS (0, 1, 2, 3, 4, 5).

11.4 Prior Anti-cancer Therapy

The prior anti-cancer therapies are collected under the “Prior Anti-Cancer Drug Therapies”, “Prior Radiotherapy” and “Prior Anti-Cancer Surgeries” eCRF pages.

The number and percentage of participants in each of the following anti-cancer therapy categories will be tabulated:

- Participants with at least one prior anti-cancer drug therapy
- Participants with at least one prior anti-cancer surgery
- Participants with at least one prior anti-cancer radiotherapy.

Prior anti-cancer drug therapy will be summarized as follows based on the number and percentage of participants with the following:

- Prior anti-cancer drug therapy regimens: missing / 1 / 2 / 3 / ≥ 4
- Prior anti-cancer drug therapy regimens: drug class and PT
- Type of prior anti-cancer drug therapy
- Intent of Therapy: Neo-Adjuvant / Adjuvant / Metastatic or Locally advanced
- Prior anti-cancer drug therapy line number: missing / 1 / 2 / 3 / ≥ 4
- Prior anti-cancer drug therapy duration

- Best response to last prior treatment: CR / PR / SD / PD / not evaluable (NE) / UNK / not applicable (NA). Best response is derived from the last treatment regimen.

The prior anti-cancer drug therapy will be summarized based on the number and percentage of participants by the Anatomical therapeutic chemical (ATC) 2nd level and PT as given from the World Health Organization Drug Dictionary (WHO-DD) March 2021 version or higher. A participant will be counted only once within a given drug class and within a given drug name, even if he/she received the same medication at different times. The summary will be sorted on decreasing frequency of drug class and decreasing frequency of drug name in a given drug class. In case of equal frequency regarding drug class (respectively drug name), alphabetical order will be used.

Prior anti-cancer surgeries will be summarized as follows based on the number and percentage of participants with the following:

- Prior anti-cancer surgery location
- Curative intent (Yes/No)
- Surgery outcome to last prior surgery: No residual tumor after resection (R0), Tumor/metastases not resected completely with microscopic residual lesions (R1), Tumor/metastases not resected completely with macroscopic residual lesions (R2), Metastases not resected (NR), Other. Surgery outcome is derived from the last surgery.

Surgeries will be displayed in terms of frequency tables: ordered by primary SOC and PT in alphabetical order.

Prior anti-cancer radiotherapy will be summarized as follows based on the number and percentage of participants with the following:

- Prior anti-cancer radiotherapy location
- Intent of Therapy: Neo-Adjuvant / Adjuvant / Metastatic or Locally advanced
- Prior anti-cancer radiotherapy duration
- Prior anti-cancer radiotherapy total dose
- Prior anti-cancer radiotherapy number of fractions
- Best response to last prior radiotherapy: CR / PR / SD / PD / NE / UNK / NA. Best response is derived from the last radiotherapy.

The listings of prior anti-cancer treatments and procedures will also be provided as follows. These will include the participant identification number, and all the relevant collected data-fields on the corresponding eCRF pages.

- Listing of prior anti-cancer drugs therapies
- Listing of prior anti-cancer surgeries
- Listing of prior anti-cancer radiotherapy

12

Previous or Concomitant Medications/Procedures

The following analyses will be performed based on the analysis set overall.

Concomitant treatments are medications, other than study treatment, which are taken by participants any time during the on-treatment period, see [Section 9.8](#).

Previous medications are medications, other than study treatment and pre-medications for study treatments, which started before first administration of study treatments.

A medication may be classified as both concomitant and previous. The respective flags will be derived based on start and end date.

Concomitant and previous treatment each will be summarized by number and percentage of participants from the “Previous and Concomitant medication and/or Therapies” eCRF. AATC 2nd level and PT will be tabulated as given from the WHO-DD March 2021 version or higher. If any previous or concomitant medication is classified into multiple ATC classes, the medication will be summarized separately under each of these ATC classes. The summary tables will be sorted by decreasing frequency of drug class and decreasing frequency of drug name in a given drug class. In case of equal frequency regarding drug class (respectively drug name), alphabetical order will be used. In case any specific medication does not have an ATC classification level 2 coded term, it will be summarized under “Unavailable ATC classification” category. Each participant will only be counted once, even if he/she received the same medication at different times.

Subsequent anti-cancer therapy

Anti-cancer therapy after end of study treatment will be summarized according to the respective eCRF page. Treatments will be categorized by means of coding and medical review. The same approach as for CMs will be applied based on ATC level 2 and PT.

Number and percentage of participants with any anti-cancer post study treatment and by type [(immunotherapy, targeted therapy, chemotherapy, radiotherapy, other)] will be presented.

Number and percentage of participants treated with targeted therapies, monoclonal antibodies and other protein kinase inhibitors as post study treatment (based upon ATC coding) will be presented including PT separately for:

- Anti-vascular endothelial growth factor (VEGFR, ATC code L01EK)
- Tyrosine kinase inhibitors (TKIs, ATC code L01EB)
- Mammalian target of rapamycin (mTOR, ATC code L01EG)
- Monoclonal antibodies (ATC code L01EX)
- Other protein kinase inhibitors (ATC code L01XC).

Summary statistics will be created for intent of therapy (Neo-Adjuvant / Adjuvant / Metastatic or Locally advanced), line number, duration, and best response across all post study treatments. For

participants who received more than one anti-cancer therapy after treatment discontinuation, the BOR among all anti-cancer therapies will be summarized.

13**Study Treatment: Compliance and Exposure**

The following analyses will be performed based on the analysis set for Avelumab and Axitinib by visit.

All dosing calculations and summaries will be based on “Avelumab Administration” and “Axitinib Administration” eCRFs pages.

No imputation of missing start dates of study treatments will be done.

In case the last date of study drugs is incomplete the date of last study drugs administration will be taken from the EOT page. A dose is regarded to be administered if the actual dose received is > 0.

Exposure duration and cumulative dose for each treatment of the combination will be summarized after being derived in days respectively as difference between last treatment date–index date +1, for Axitinib (days unit) and (last treatment date – index date +14) for Avelumab and the sum of the actual doses of study drugs received overall. For Avelumab, duration will also be expressed in terms of cycles and derived as (last treatment date – index date +14)/14 considering each cycle duration of 2 weeks.

The summary of treatment exposure will include the following information:

- Exposure duration (days/cycles)
- Cumulative dose (milligrams)
- Overall actual dose intensity (DI) will be derived as overall actual cumulative dose (mg) / exposure duration (cycles or days for Avelumab or Axitinib respectively)
- Avelumab relative DI will be derived as $100 \times [\text{overall actual DI}] / [\text{intended DI}] = 100 \times [\text{overall actual DI}] / [\text{overall planned cumulative dose (mg) / exposure duration (cycles)}]$
- Axitinib relative DI will be derived as $100 \times [\text{overall actual DI}] / [\text{intended DI}] = 100 \times [\text{overall actual DI}] / [\text{overall planned cumulative dose (mg) / exposure duration (days)}]$

Percentage of patients with at least one dose adjustment over the study will be presented for each treatment of the combination descriptively along with frequency of adjustments (Dose adjusted, No dose) and detailed reasons (AEs, Missed dose [applicable for No dose only], Other).

14**Efficacy Analyses**

The following analyses will be performed based on the analysis set.

